## 7 PARTICIPANT ENROLLMENT

#### 7.1 Consenting Participants

Informed consent for participation in the study must be obtained before performing any study-specific procedures.

Informed Consent Forms for enrolled participants and for participants who are not subsequently enrolled will be maintained at the study site in secure study files. Consent will be obtained by trained research study staff trained in taking informed consent. The study will be explained with the opportunity for the participant to ask questions. If a participant wishes to enter the study, a consent form will be completed and signed.

## 7.2 Screening for Eligibility

Informed consent will be obtained prior to any screening assessments. Screening assessments (Visit 1; V1) will be performed within 2 weeks (-14 days) prior to the Baseline visit (V2) and will include: medical history and medication use, complete physical examination including height, weight, vital signs, and 12-lead ECG, a neurological examination, nasal inspection, laboratory testing, including blood sample for a comprehensive metabolic panel, complete blood count, chemistry, lipid panel, and liver function test, as well as urinalysis. Urine pregnancy test will be performed on WOCBP. All screening evaluations must be completed and reviewed to confirm that participants meet all eligibility criteria before entering baseline period on Day -28. Inclusion and exclusion criteria will be reviewed at Screening (V1), Baseline visit (V2), and Randomization visit (V3) to make sure nothing changed. Enrolled subjects will be asked to undergo a 4 week (Day -28 to 0) baseline period.

Eligible subjects will return to clinic on Day -28 (V2) for baseline assessments and will be sent home to record their migraine events and acute migraine medication use over the 28 day baseline period using a diary. Subjects will return to clinic on Day 0 (V3) for randomization upon confirming continued eligibility. Subjects are randomized at V3 upon confirming the inclusion/exclusion criteria and the entry criteria of 4-14 migraine headache days and 80% diary compliance during the baseline period.

For subjects who do not meet the 80% daily diary compliance but otherwise meet the 4-14 migraine days requirement during the baseline period, they can be provided additional opportunities to meet the 80% diary compliance requirement to enable continued eligibility for randomization. The following allowances can be made per investigator judgement on a case by case basis:

- If the anticipated diary compliance is slightly less than 80% or short by 4 daily diary entries by the day before the randomization visit, subjects can enter up to 4 additional days of diary entries (over the ±3 day visit window specified in the schedule of events in the protocol) as part of the baseline period and reschedule the randomization visit immediately after this period. This provides up to 7 additional days of diary entries to fulfill compliance. Twenty-eight days prior to the new randomization visit day can be re-evaluated for the baseline period.
- If the anticipated diary compliance is short by more than 4 daily diary entries by the day before the randomization visit, the investigator has the option to shift the baseline period (i.e., reset) to a randomization visit date that allows subjects to record the additional days of diary entries that fulfills 80% compliance and resets the baseline period 4 weeks back from the new randomization visit day.

• The investigator has the option to request subjects to repeat the baseline period (i.e., rebaseline) by entering 28 additional days of diary entries as part of a new baseline period and re-evaluate the baseline period 4 weeks back from the new randomization visit day.

All screening assessments are listed in the Schedule of Events Table (Appendix A). A participant must meet all inclusion criteria, and none of the exclusion criteria, to be enrolled and randomized in this study. The Investigator and team will maintain a screening log to record details of all persons screened and to confirm eligibility or record reasons for screening failure, as applicable.

## 7.3 Study Withdrawal and Withdrawal From Investigational Product and Stopping Criteria

A participant may withdraw from the study at any time at his/her own request, or may be withdrawn at any time at the discretion of the Investigator.

Reasons for withdrawal (participants who refuse to complete any remaining study visits) or discontinuation (participants who prematurely stop the application) at any time during the study may include, but are not limited, to the following:

For safety reasons, either at the discretion of the Investigator or at the participant's request

For protocol violations at the discretion of AOBiome

Due to concomitant therapy that could interfere with the results of the study (the Investigator will report all such information on the CRFs and decide, in accordance with AOBiome, whether the participant is to be withdrawn).

The reason for participant study withdrawal will be recorded in the electronic Case Report Form (eCRF). Data from participants withdrawing from the study will be considered evaluable up to the point at which they are withdrawn using the same criteria for evaluability as for participants who complete the study.

#### 7.4 Screen Failures

Data for screen and baseline failures will be collected in source documentation at the site but will not be transmitted to AOBiome.

#### 7.5 Early Termination

Participants who have discontinued the study early will be evaluated by the Investigator at the Early Termination Visit. See the list of assessments to be performed at the Early Termination Visit in the Schedule of Events Table (Appendix A). Participants with ongoing AEs or SAEs believed to be possibly related to investigational product (IP) will continue to be followed until resolution or for 30 days as warranted by the nature of the AE.

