## 3.2 Secondary Objectives

- To evaluate the efficacy of B244 relative to vehicle for migraine prevention in subjects with episodic migraine
- To continue to assess safety during the 28 day follow-up period.

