#### 5 STUDY DESIGN

- This is a prospective, randomized, vehicle-controlled, double-blind, 3-arm parallel assignment study assessing the safety, tolerability, and efficacy of B244 delivered as an intranasal spray for preventive treatment in subjects with episodic migraine.
- This study will enroll 303 subjects.
- Enrolled subjects will undergo a 28 day baseline period to establish baseline headache frequency and characteristics.
- Subjects will be randomized at the end of the baseline period. Randomization will be 1:1:1 so that equal number of subjects will be treated in each Arm of the study.
- Subjects will be trained for in-home treatment/assessment on the use of the nasal spray, and apply their first dose of treatment under the supervision of study personnel on site. Subjects will remain under observation at the study site for 1 hour post dosing. Subjects will then be dispensed study medication for 12 weeks of at home dosing (either 1x10° cell/ml; 4x10° cells/ml; or vehicle). While at home, subjects will dose twice daily (am and pm) for 12 weeks during the prevention treatment phase. Subjects will be asked to visit the site every 4 weeks during the 12 week treatment period and 4 week follow-up.
- Daily assessments will be made during the 12 week double-blind treatment period for safety, tolerability and efficacy. Additional safety assessments will be made during the follow-up period 28 days after last treatment. Subjects will record their dosing, migraine incidence/severity/duration, and rescue (acute migraine specific) medications using a study diary.

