#### **8.14 Rescue Medications**

Use of rescue medication is allowed throughout the study with subjects' usual acute migraine specific medication of choice to relieve their symptoms of an acute attack of migraine (usually a triptan, possibly NSAID or analgesic) and recorded in the eCRF. Subjects should avoid intranasal formulations of rescue medications. Subjects should not initiate a preventive medication during study and are prohibited from using any migraine-specific medications as preventive treatment between acute episodes. Subject may not start additional non-randomized medication and should immediately alert the study site PI. Subjects are encouraged not to start any new acute migraine/headache treatments during the course of the study and may be withdrawn from the study pending discussion with the PI and sponsor medical monitor in such cases. If discontinuation is necessary, this would be considered an early termination. A list of allowed rescue medications includes:

- All acute/abortive medications (excluding intranasal formulations) such as triptans (oral
  or injection route only) and ergot containing preparations (ergotamine tartrate, DHE 45
  by IM, SQ, IV) up to 10 days per month
- NSAIDs and analgesics (e.g., acetaminophen, acetylsalicylic acid, combination analgesics) for migraine and non-migraine headaches up to 14 days per month
- Opioid/barbiturate containing medications of up to 4 days per month

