## 10.6.7 Follow-Up Week 16 (End of Study) (V7; Study Day 112) (±3 Days Visit Window)

Every attempt should be made to complete all visits during the defined window periods. Subjects who do not complete all required study visits and withdraw from the study will be asked to complete an End of Study Evaluation.

- record concomitant medications
- · obtain in clinic blood pressure, heart rate, respiratory rate
- brief physical exam
- neurological exam
- body weight
- blood collection for biomarkers
- nasal inspection
- nasal fluid collection for biomarkers
- study AEs
- study diary
- migraine pain intensity score
- HIT-6
- MSQL
- CGI
- subject satisfaction survey

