#### 14.4.2 Adverse Events

All adverse events (AEs) recorded during the study through the date of randomization through 28 days after the last dose of study drug will analyzed.

All AE's will be coded according to Medical Dictionary for Regulatory Activities and summarized using System Organ Class (SOC) and Preferred Term (PT).

AE's will be summarized using incidence rates. Therefore, each subject will only contribute once for a given adverse event SOC or PT.

A summary of the incidence of any adverse event, SAE, and adverse events leading to discontinuation will be presented. Summaries will display, by treatment, the incidence of patients with events, the frequency of patients with events within each primary system organ class and by preferred terms. For each preferred term and each system organ class a patient

will be counted only once. For summaries on severe or drug-related AE, for a given patient, the highest severity or relationship for a specific preferred term will be considered.

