## 15.3 Time Period, Frequency, and Method of Detecting AEs and SAEs

All AEs occurring after administration of the first dose of study medication and on or before the final assessment must be reported as AEs. All AEs must be recorded irrespective of whether they are considered drug-related.

At each assessment in the period defined above, AEs will be evaluated by the Investigator and recorded.

Any AEs already documented at a previous assessment and designated as ongoing, should be reviewed at subsequent assessments as necessary. If these have resolved, this should be documented. Changes in intensity or frequency of AEs should be recorded as separate events (i.e., a new record started).

The recording of AEs and SAEs are described in Section 15.4 ("Recording of AEs and SAEs").

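### No adverse-event contact is scheduled up to 28 days after the last dose for subjects who leave the study early, although section 14.4.2 analyses that window

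*Protocol*

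**What the plan says.** Safety is the primary endpoint (Protocol 4.1), and safety after the 28-day follow-up is a secondary endpoint (4.2). The matching objective is "To continue to assess safety during the 28 day follow-up period" (3.2). Section 5 ties the follow-up to the end of dosing: "Additional safety assessments will be made during the follow-up period 28 days after last treatment". Section 14.4.2 analyses adverse events "through the date of randomization through 28 days after the last dose of study drug will analyzed".

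Collection is described differently. Section 15.3 requires reporting of events that occur after the first dose and "on or before the final assessment must be reported as AEs". The only visit scheduled after treatment is V7, at Day 112 (10.6.7, Appendix A). For early leavers, section 7.5 states "Participants who have discontinued the study early will be evaluated by the Investigator at the Early Termination Visit". Sections 10.6.8 and 12.5 list or refer to the assessments for that visit, and none of the three times it from the last dose.

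Other passages bear on what happens next:

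- Section 7.5 keeps ongoing, possibly related events in follow-up until they resolve or for 30 days. Section 15.4 follows possibly related events to resolution.
- Section 15.7 keeps serious events that the investigator attributes to the product reportable at any time after dosing stops.
- Section 10.6.7 says that subjects who miss visits and "withdraw from the study will be asked to complete an End of Study Evaluation", without saying when.
- Section 12.2 records events related to the intranasal route up to the end of follow-up.

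**The concern.** The analysis window is defined from the last dose, while collection is defined by visits. The two coincide for a subject who completes treatment, because V7 is nominally 28 days after V6. For a subject who leaves during treatment, the Early Termination visit may fall on or near the last-dose date, and no later contact is expressly scheduled at which new events would be asked about.

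This matters because the gap lies in the primary endpoint, in the period that a secondary objective sets out to observe. The product is a live organism, and section 12.2 lists infectious complications among the events monitored at follow-up. A crude incidence would count an early leaver in the denominator as if the whole window had been seen. The analysis stage cannot repair this, since no statistical analysis plan can recover events that were never solicited.

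**Working it through.** **1. Is the Early Termination visit the final assessment?** No sentence says so outright. Section 10.3 names V7 and the Early Termination visit as alternatives for the satisfaction survey, and Appendix A footnote 18 allows the survey at the latter only on discontinuation or withdrawal. Section 7.3 treats a withdrawn subject's data as evaluable up to the point of withdrawal. Together these support reading the Early Termination visit as the closing visit for someone who leaves. The untimed End of Study Evaluation in 10.6.7 leaves some doubt.

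**2. What is still captured after that visit?**

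| Event after the Early Termination visit | Provision | Captured? |
|---|---|---|
| Ongoing, possibly related | 7.5, 15.4 | Followed |
| New, serious, attributed to product | 15.7 | Reportable if it comes to the investigator's attention |
| New, serious, not attributed to product | None scheduled | Not systematically |
| New, non-serious | None scheduled | Not systematically |

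Section 15.3 requires recording regardless of relatedness, so the last two rows belong to the intended data.

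**3. Who is affected?** Section 7.3 distinguishes stopping the product from refusing further visits. Section 7.5 concerns those who discontinued the study. Section 8.14, on subjects who start a new acute treatment, says "If discontinuation is necessary, this would be considered an early termination". Section 10.3 and footnote 18 use discontinuation and withdrawal side by side. The gap is therefore clear for study-leavers and unresolved for subjects who only stop the product.

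**4. Size.** Inputs: 303 enrolled, target 264, drop-out 10-15% (6.1, 14.1), window 28 days (14.4.2).

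- Plan's own figures: 303 − 264 = 39, and 39/303 = 12.9%, inside the stated range.
- Early leavers: 0.10 × 303 ≈ 30; 0.15 × 303 ≈ 45.
- Planned post-dose subject-days: 303 × 28 = 8,484.
- Days without scheduled collection if the visit falls on the last-dose date and nothing is captured later: 30 × 28 = 840 (9.9%); 39 × 28 = 1,092 (12.9%); 45 × 28 = 1,260 (14.9%).

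**5. Effect on an observed rate (illustration only).** If a fraction f of an arm has an unobserved window and the true post-dose event rate is p, the observed rate is p(1 − f). Assume p = 5%, with f = 20% in one arm and 10% in another; none of these values is in the protocol. The observed rates are 5% × 0.80 = 4.0% and 5% × 0.90 = 4.5%. With 303/3 = 101 per arm, that loses 101 × 0.05 × 0.20 ≈ 1.0 and 101 × 0.05 × 0.10 ≈ 0.5 subjects with an event.

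**6. Completers.** Nominal gap from V6 to V7: 112 − 84 = 28 days. With ±3 days on each visit, the shortest gap is 109 − 87 = 22 days and the longest is 115 − 81 = 34 days. Product application is listed at V6 (10.6.6), so if the last dose is taken at V6, observation can end before the 28 days that 14.4.2 analyses.

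**The case against.** A reader might infer that adverse-event collection simply ends at the Early Termination visit. The documents do not say that. Sections 7.5, 15.4 and 15.7 keep important classes of event in follow-up, section 12.2 runs recording of route-related events to the end of follow-up, and 10.6.7 asks withdrawers for a further evaluation of unstated timing. Follow-up contacts for one event may also bring new ones to light. This objection stands: the gap is limited to new events that are non-serious or not attributed to the product.

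A reader might also infer that everyone who stops the product is lost. Section 7.3 separates the two groups, and no passage removes a product-only stopper from V7. This stands too; the protocol is unclear here, not demonstrably deficient.

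A third tempting reading is that the loss falls chiefly on those who stopped for harm and so biases the comparison toward safety. Safety is the first reason listed in 7.3, but the protocol gives no rate by reason or by arm, and subjects with ongoing possibly related events are the ones 7.5 keeps under follow-up. Nor does section 12.2 support a claim about late effects through its word for delayed reactions, which there means onset more than 30 minutes after administration.

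Finally, some leavers cannot be reached whatever the schedule says, and those who leave after Day 84 already have part of their window observed. That makes the figures upper bounds. It does not remove the mismatch between the window analysed and the contacts scheduled. Section 12.5 asks for a status check by telephone or other means, but only for those who refuse the Early Termination assessments, and it is not set at 28 days after the last dose.

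**Conclusion.** The point holds in limited form. For subjects who leave the study early, the protocol analyses adverse events to 28 days after the last dose but expressly schedules no contact at which new events in that window would be elicited. It concerns at most about 30-45 of 303 subjects and up to 840-1,260 of 8,484 planned post-dose subject-days (9.9% to 14.9%). This assumes that the Early Termination visit coincides with the last dose, that every drop-out occurs during treatment, and that nothing is captured afterwards.

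The size and direction of any between-arm bias depend on differential stopping, for which the documents give no figure; the 4.0% versus 4.5% illustration shows the mechanism only. The completer window of 22 to 34 days is a secondary point. No sample-size or power figure is affected. The change is worth making because it touches the primary endpoint, cannot be made good at analysis, and is cheap.

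**What to change.** - In 7.5, 10.6.8 and Appendix A, add one adverse-event contact, by telephone if needed, 28 days after the last dose for every dosed subject who leaves early and has not withdrawn consent.
- State whether subjects who only stop the product continue to V7, and use the terms for discontinuation and withdrawal consistently in 7.3, 7.5, 8.14, 10.3 and Appendix A footnote 18.
- Align the end of adverse-event reporting in 15.3 and 12.2 with the 28-day window in 14.4.2.
- Reconcile 7.5, 10.6.7 and 15.7, including when the End of Study Evaluation takes place and how it relates to the Early Termination visit.
- Tabulate by arm the number of subjects observed for the full 28 days, so that any shortfall, including one from the V6 and V7 visit windows, is visible.

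The cost is a small amendment and one short contact for about 30-45 subjects.

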## 10.6.8 Unscheduled/Unanticipated or Early Termination Study Visit

If an event arises that requires patient to come in to the research center, subjects should be scheduled for the Unscheduled visit.

During the visit, the following will be obtained:

- · record concomitant medications
- obtain in clinic blood pressure, heart rate, respiratory rate
- brief physical exam
- neurological exam
- body weight
- blood collection for biomarkers
- nasal inspection
- obtain study medication weight for Investigational Product compliance
- study counseling
- laboratory testing (blood for metabolic panel, hematology, clinical chemistry, lipid panel, liver function test, urinalysis)
- nasal fluid collection for biomarkers
- study AEs
- study diary
- migraine pain intensity score
- MIDAS
- HIT-6
- MSQL
- CGI

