#### 11.5 12-Lead ECG

12-lead ECG will be taken at Screening (V1), Randomization (end of 4 week baseline period; V3), and Prevention Treatment Week 12 (V6). Standard 12-lead ECGs will be performed according to the site SOPs. ECGs should be performed after the subject has been resting supine for 5 minutes. The ECG will include all 12 standard leads and a Lead II rhythm strip on the bottom of the tracing. The ECG will be recorded at a paper speed of 25 mm/sec. The following ECG parameters will be collected: PR interval, QRS interval, QT interval, and QTc interval (QTcB; Bazetts correction). All ECGs must presence of abnormalities.

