### 11.7 Laboratory Assessments

Blood sample will be taken for hematology and clinical chemistry, including standard metabolic panel, complete blood count (CBC), clinical chemistry, lipid panel, and liver function test. Approximately 15 ml of whole blood will be drawn. Urinalysis will be performed as part of safety labs. Laboratory assessments will be made at Screening (V1), Randomization (end of 4 week baseline period; V3), Prevention Treatment Week 12 (V6), and at Unanticipated/Early Termination Visit should one occur.

Blood samples should be taken using standard venipuncture techniques. Blood sampling will be performed according to the site SOPs.

The following laboratory variables will be determined: Fasting glucose, Uric acid, BUN (blood urea nitrogen), Creatinine, BUN/creatinine ratio, eGFR (estimated glomerular filtration rate), Sodium, Potassium, Chloride, Calcium, Total protein, Bicarbonate, Albumin, Bilirubin, Alkaline phosphatase, AST (aspartate aminotransferase), ALT (alanine transaminase), total cholesterol, HDL, LDL, triglycerides, CBC (standard panel including RBC, hemoglobin, hematocrit, platelets, and WBC, including neutrophils, lymphocytes, monocytes, eosinophils, basophils), and proteinurea.

Any value outside the normal range (except those affected by not fasting) will be flagged for the attention of the Investigator or designee at the site. The Investigator or designee will indicate whether or not the value is of clinical significance. If the result of the clinical chemistry test from the samples taken during the screening phase is indicated as clinically significant, the study subject will NOT be allowed into the study.

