## 12.5 Subject Withdrawal Criteria

A subject may withdraw from the study at any time at his/her own request, or may be withdrawn at any time at the discretion of the Investigator for safety, behavioral, or administrative reasons.

Reasons for withdrawal (subjects who refuse to return for any remaining study visits) or discontinuation (subjects who prematurely stop the application) at any time during the study may include, but are not limited, to the following:

For safety reasons, either at the discretion of the Investigator or at the subject's request For protocol violations at the discretion of AOBiome

Due to concomitant therapy that could interfere with the results of the study (the Investigator will report all such information on the CRFs and decide, in accordance with AOBiome, whether the subject is to be withdrawn).

All premature discontinuations and their causes must be carefully documented by the Investigator on the CRF or if needed on the AE form.

If, for any reason, a subject is withdrawn before completing the final visit, the reason for termination will be entered on the CRF. All data gathered on the subject prior to termination will be made available to AOBiome. Subjects not completing the entire study should be fully evaluated when possible. The appropriate CRFs should be completed.

If the subject chooses to withdraw before completing the study, the subject should notify the study coordinator who will instruct the subject on completion of assessments for Unanticipated/Early Termination visit (Appendix A). For subjects who refuse to complete the assessments for their early termination, every attempt must be made to check on their status, using any mode of communication such as telephone, email, fax, or text.

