## CONFIDENTIAL

Study diary 	X	X	X	X	X	X	X	X
Migraine pain intensity score	X	X	X	X	X	X	X	X
MIDAS 		X	X			X		X
HIT-6 		X	X	X	X	X	X	X
MSQL 		X	X	X	X	X	X	X
CGI 		X	X	X	X	X	X	X
Subject Satisfaction Survey							X	X 

- 1. Informed consent can be obtained up to 14 days prior to the baseline visit (V2).
- 2. Inclusion and exclusion criteria will be reviewed at Screening (V1), Baseline (V2), and Randomization (V3) visits to make sure nothing changed.
- 3. Blood samples for biomarkers will be collected and processed on site. Serum/plasma samples will be frozen onsite and shipped to the Central lab for storage.
- 4. Subject's demographic data and medical history are blinded to the statistician for randomization and treatment assignment. Only subjects with 4-14 migraine headache days per month during baseline period (28 days between V2 and V3) will be randomized.
- 5. Nasal inspection will include clinical examination of the nasal mucosa, sinuses, and upper airway using an otoscope.
- 6. Subjects will be trained for in-home treatment/assessment on the use of the nasal spray, and have their first dose of treatment on site (V3). Subjects will remain onsite for observation for 1 hour post dosing. Subjects will then be dispensed study medication for 12 weeks of at home dosing.
- 7. Weight of individual IP bottles will be obtained at visits V3 (before and after first dose), V4, V5, V6, and unanticipated/early termination visit.
- 8. Subjects will be counseled on the application of the nasal spray, study diary, and answer any questions.
- 9. Fasting blood sample for a comprehensive metabolic panel, complete blood count, chemistry, lipid panel, and liver function test-15 ml. Also includes urinalysis. Patients should fast for at least 8 hours before the test. Blood will be shipped to the central lab for processing.
- 10. Urine pregnancy test to be done on WOCBP.
- 11. Intranasal strip will be used to collect nasal fluid for inflammatory cytokines. Optionally, nasal fluid may be evaluated for nasal microbiome (e.g., PCR) to confirm presence of B244.

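### The Early Termination visit repeats every Week 12 safety assessment except the 12-lead ECG, so subjects who leave before Week 12 have no scheduled ECG after the first dosing day

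*Protocol*

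**What the plan says.** Section 11.5 fixes the ECG schedule: "12-lead ECG will be taken at Screening (V1), Randomization (end of 4 week baseline period; V3), and Prevention Treatment Week 12 (V6"). The visit lists in 10.6 match it, with an ECG at V1, V3 and V6 and none at V2, V4, V5 or V7. The first dose is given at V3; Appendix A, footnote 6, has subjects "have their first dose of treatment on site (V3").

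For subjects who leave early, section 7.5 points to the schedule: "See the list of assessments to be performed at the Early Termination Visit in the Schedule of Events Table (Appendix A"). Section 10.6.8 spells out the visit under "During the visit, the following will be obtained". Its list has no ECG but does contain "laboratory testing (blood for metabolic panel, hematology, clinical chemistry, lipid panel, liver function test, urinalysis"). Section 11.7 confirms that laboratory testing is done at "Prevention Treatment Week 12 (V6), and at Unanticipated/Early Termination Visit should one occur".

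Two other statements bear on early leavers. Section 10.6.7 says: "Subjects who do not complete all required study visits and withdraw from the study will be asked to complete an End of Study Evaluation". Section 12.5 says: "Subjects not completing the entire study should be fully evaluated when possible".

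**The concern.** The trial's purpose is safety relative to vehicle, and safety is the first reason for withdrawal given in 7.3 and 12.5. An assessment made once on treatment, at Week 12, and not repeated when a subject leaves sooner is observed only in those who stayed. If leaving is related to tolerability, the ECG comparison between arms is then restricted to subjects who tolerated the spray.

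The omission also looks unintended. Physical examination, nasal inspection, laboratory tests, both biomarker samples and all four questionnaires and scales are extended to the Early Termination visit in their own method sections. The ECG is not, and the protocol gives no reason. An ECG that was not taken cannot be recovered at analysis.

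**Working it through.** **1. Where the ECG is scheduled.** Section 10.6 set against sections 11.2 to 11.7:

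| Assessment | Scheduled visits | Early Termination (10.6.8) |
|---|---|---|
| 12-lead ECG | V1, V3, V6 | no |
| Laboratory tests | V1, V3, V6 | yes |
| Vital signs | V1 to V7 | yes |
| Physical examination | V1 to V7 | yes |
| Neurological examination | V1 to V7 | yes |
| Body weight | V1 to V7 | yes |
| Nasal inspection | V1 to V7 | yes |
| Adverse events | V1 to V7 | yes |

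The laboratory row is the closest comparison: same scheduled visits, opposite treatment at Early Termination.

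**2. V6 list against the Early Termination list.** V6 (10.6.6) has 19 items and Early Termination (10.6.8) has 18.
- In V6 but not in Early Termination: 12-lead ECG and product application.
- In Early Termination but not in V6: counselling.
- Check: 19 - 2 + 1 = 18.

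Product application is not a safety assessment, and its absence from a termination visit needs no explanation. The ECG is the only V6 safety assessment left out.

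**3. Is the blank genuine?** Some rows of the Appendix A table are incomplete in the text available for this review, so an empty cell there proves little alone. Sections 10.6.8 and 11.5 independently give the same answer for the ECG.

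**4. Is there another route to a scheduled ECG?** The End of Study evaluation in 10.6.7 has none. V4 and V5 have none. The V3 list does not say whether the ECG comes before or after the first spray, so the accurate statement is that no ECG is scheduled after the first dosing day. A subject who stops the spray but still attends V6 does have one.

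**5. How many subjects.** Section 14.1 enrols 303 to retain 264 with 10-15% drop-out.
- Reproducing the plan: 264 / 0.90 = 293.3, so 294; 264 / 0.85 = 310.6, so 311. The stated 303 lies between and implies (303 - 264) / 303 = 39 / 303 = 12.9%.
- Subjects leaving: 303 x 0.10 = 30.3 and 303 x 0.15 = 45.5, or about 30 to 45 (39 at the implied rate).
- Per arm of 303 / 3 = 101: 101 x 0.10 = 10.1 and 101 x 0.15 = 15.2, or about 10 to 15.

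These figures assume that all drop-out falls before V6. They are a maximum at the planned rate. Anyone who leaves between V6 and V7 already has the V6 ECG. The number the fix can recover is lower again, because some subjects will decline the termination visit, as 12.5 foresees.

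**6. What cannot be calculated.** The protocol gives no expected rate of ECG abnormality and no rate of stopping because of one. No figure for the resulting bias follows from the document.

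**The case against.** The strongest reply is that this is a consistent choice about a supporting measure. Sections 11.5, 10.6.8 and Appendix A agree. Section 4.1 builds the primary endpoint from adverse events, physical and neurological examination, and vital signs, and all of these are collected at Early Termination. All of that stands. A reader might infer that the protocol contradicts itself or that the primary endpoint is compromised; the text supports neither.

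A reader might also infer that an ECG change leading a subject to stop would never be recorded. That goes too far. Section 15.4 puts all clinical events on the adverse event page, 12.5 requires the cause of every premature discontinuation to be documented, 14.4.4 summarises adverse events leading to discontinuation, and section 20 allows extra safety assessments case by case. What remains missing is narrower: a routine ECG that does not depend on symptoms or site judgement. Ad hoc ECGs would not be comparable between arms and would tend to miss silent changes in the PR, QRS and QTc intervals that 11.5 collects.

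Section 12.5 might be read as breached by its call for a full evaluation. It is not, because the same section then refers withdrawing subjects to the Appendix A list.

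Last, Early Termination ECGs come at varying exposure, and possibly some time after the last dose, so simply merging them with V6 would mix unlike recordings. This objection is sound and shapes the fix.

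**Conclusion.** The gap is real but moderate. Under the protocol as written, dosed subjects who leave before V6 have no scheduled ECG after Day 0, and the scheduled on-treatment ECG data describe only those who reach Week 12. The number affected is at most about 30 to 45 of 303 (10 to 15 per arm) if drop-out is as planned and all of it occurs before V6, and fewer otherwise.

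The loss is of comparable routine ECG data, chiefly silent interval changes, in early leavers. It does not touch the primary endpoint as defined, and it does not remove symptomatic events from the record. It deserves correction because the remedy is cheap, the omission runs against how nearly every other assessment is handled, and the missing data cannot be obtained later.

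**What to change.** Add the 12-lead ECG to the Early Termination assessments in 10.6.8, 11.5 and the Appendix A column, limited to dosed subjects who terminate before V6. Since 10.6.8 and Appendix A share one list between unscheduled and termination visits, a footnote is needed so that other unscheduled visits are not affected. Appendix A, footnote 18, already does this for the satisfaction survey.

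In the analysis, summarise the last on-study ECG (V6 or Early Termination) by arm, alongside a V6-only summary. Show time on treatment and time since last dose for the Early Termination recordings, so that differing exposure is visible.

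The cost is at most about 30 to 45 ECGs, each in place of a V6 ECG that would not otherwise be done, at sites that already record ECGs at three visits. It needs an amendment with ethics approval under section 26, and it helps only subjects who terminate after the amendment takes effect. It will not recover those who decline the visit.
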